## 7.4.4 Blinding of Study Device

Injections of the study device are performed by the unblinded Treating Investigator. The blinded Evaluating Investigator is not allowed to retrieve study supplies or to be present during opening of the study supplies or during the injections. The Treating Investigator is not to have any discussion with the Evaluating Investigator or subjects regarding the treatments.

Subjects are blinded to treatment assignment. Subjects are physically masked (blindfolded) just prior to and during all injection procedures to prevent observation of the syringes containing study device.

Subjects, investigators, the Sponsor's staff conducting the study, and members of the administrative team will not have access to individual subjects' treatment assignments. In the event of an emergency that requires breaking of the study blind, the randomization code will be maintained by each investigator that can be opened to reveal the study device.

See Section 7.9.10.2 for a description of the method of unblinding a subject during the study if such action is warranted.

## 7.4.5 Method of Packaging, Labeling, Storage, and Dispensing

For PN40082, one 1.0 mL syringe is packaged along with two fine-gauge needles (30G) in an easy-open tray. Each syringe is equipped with a Luer-Lok as well as a custom finger grip and plunger rod. The syringes contain a peelable label to be placed on the subject record for tracking purposes. Two trays are packaged in a carton. A label that includes the protocol number and Sponsor name will be attached to each carton.

For RV001 with topical anesthetic, one 1.0 mL syringe is packaged along with two fine-gauge needles (27G) in an easy-open tray. 30G fine-gauge needles will be provided in bulk by the Sponsor for use instead of the 27G needles. Each syringe is equipped with a Luer-Lok as well as a custom finger grip and plunger rod. The syringes contain a peelable label to be placed on the subject record for tracking purposes. Two trays are packaged in a carton. A label that includes the protocol number and Sponsor name will be attached to each carton. Bulk commercial supplies of LMX4 will be provided.

For RV001, one 1.0 mL syringe is packaged along with two fine-gauge needles (27G) in an easy-open tray. 30G fine-gauge needles will be provided in bulk by the Sponsor for use instead of the 27G needles. Each syringe is equipped with a Luer-Lok as well as a custom finger grip and plunger rod. The syringes contain a peelable label to be placed on the subject record for tracking purposes. Two trays are packaged in a carton. A label that includes the protocol number and Sponsor name will be attached to each carton. To confirm use of the 30G needles, the 27G needles should remain in the retained packaging for reconciliation.

All study device will be stored in a climate-controlled, limited access area.

The investigator agrees to store and administer the study device only at the site(s) listed on Form FDA 1572 (or investigator agreement/statement). The investigator, sub-investigator(s), or qualified designees also agree that the study device will be administered only to subjects who have provided written informed consent and have met all entry criteria. The study device may not be used for any purpose other than as stated in the protocol.

## 7.4.6 Study Device Accountability

Study device will be available on site for each subject. Receipt of study device will be documented and confirmed via the Investigational Product Receipt Form. All study device must be kept in a locked area with access restricted to designated study personnel in a climate-controlled, limited access area. The administration of study device will be recorded on the Study Device Dispensing Log. The site monitor will periodically check the supply of study device held by the investigator or pharmacist to ensure accountability. At study conclusion, all unused investigational product will be returned to the Sponsor and documented using the Investigational Product Return Form.

Inventory records must be readily available for inspection by the study monitor and/or auditor, and open to inspection by regulatory authorities at any time.

#### 7.4.7 Concomitant Medications

All medications and other treatments taken by the subject during the study and 6 months prior to Visit 1 for subjects who did not participate in PRO 2018-03 are to be recorded on the CRF using their generic name, if known, with the corresponding indication. The medications to be recorded include prescription and over-the-counter (OTC) medications and dietary supplements. All medications taken on a regular basis, including vitamins, aspirin, and acetaminophen, should be recorded prior to use of the study device.

The use of any concomitant medication must relate to the subject's documented medical history, prophylaxis, or an AE.

#### 7.4.7.1 Precautions

Subjects should be given the following additional instructions:

- Subject should minimize or avoid excessive natural or artificial sunlight exposure and extreme cold weather
- Subjects should avoid epilation, laser, mechanical or chemical peeling procedures during the study

## 7.4.7.2 Medications and Treatments Prohibited During the Study

Subjects will be advised to avoid the following for the duration of the study:

- Facial plastic surgery or permanent facial implants (e.g., polymethylmethacrylate, silicone, polytetrafluoroethylene, polyacrylamide, lifting threads) anywhere in the face or neck
- Semi-permanent dermal filler treatment (e.g., calcium hydroxylapatite, poly-L-lactic acid) in the lower face (below the orbital rim)
- Other hyaluronic acid filler materials or collagen-based filler materials below the orbital rim
- Facial tissue augmentation with fat injections, botulinum toxin injections in the lower face (below the orbital rim), mesotherapy, or cosmetic procedures in the face or neck (e.g., face-lift, laser, photo-modulation, intense pulsed light, radio frequency,

dermabrasion, moderate or greater depth chemical peel, microneedling, or other ablative procedures)

- Use of any lip plumping products or devices
- Use of any OTC or prescription, oral or topical, anti-wrinkle products for the lips or around the mouth (Subjects who have been on a regimen of such products for at least 90 days must continue their regimen throughout the study.)

## 7.4.7.3 Concomitant Medications and Treatments Allowed During the Study

Permitted medications/treatments include any concomitant medication/treatment not listed below.

- Facial plastic surgery or permanent facial implants (e.g., polymethylmethacrylate, silicone, polytetrafluoroethylene, polyacrylamide, lifting threads) anywhere in the face or neck
- Semi-permanent dermal filler treatment (e.g., calcium hydroxylapatite, poly-L-lactic acid) in the lower face (below the orbital rim)
- Facial tissue augmentation with fat injections, botulinum toxin injections in the lower face (below the orbital rim), mesotherapy, or cosmetic procedures in the face or neck (e.g., face-lift, laser, photo-modulation, intense pulsed light, radio frequency, dermabrasion, moderate or greater depth chemical peel, microneedling, or other ablative procedures)
- Use of any lip plumping products or devices
- Use of any OTC or prescription oral or topical anti-wrinkle products for the lips or around the mouth (subjects who have been on a stable regimen of such products for at least 90 days must continue their regimen throughout the study.)

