#### 7.3.2 Exclusion Criteria

Subjects who meet any of the following criteria will be excluded from the study:

- 1. Women who are pregnant, lactating, or planning a pregnancy.
- 2. Subjects with a known history of allergy, anaphylaxis or hypersensitivity to injectable hyaluronic acid products, local anesthetics of the amide type such as lidocaine, or to latex.
- 3. Subjects with a significant ongoing adverse event from PRO 2018-02 or PRO 2018-03 that in the opinion of the investigator could be worsened by participation in this study.
- 4. Subjects that experienced an SAE, AESI, visual changes or other serious medical conditions during PRO 2018-02 or PRO 2018-03.
- 5. Subjects with abnormal vision evaluations (Confrontational Visual Fields, Ocular Motility) or abnormal Snellen Visual Acuity at Visit 1 pre-treatment as defined in section 7.6.5 and Appendix 5.
- 6. Subjects who are unable to withhold thrombolytics, or inhibitors of platelet aggregation or nonsteroidal anti-inflammatory drugs (NSAIDs, e.g., aspirin, ibuprofen) or other substances known to increase coagulation time (e.g., herbal supplements with garlic or gingko) within 10 days before AND after any injection session.
- 7. Subjects with clinically significant organic disease including clinically significant cardiovascular, hepatic, pulmonary, neurologic, or renal disease or other medical condition, serious intercurrent illness, or extenuating circumstance that, in the opinion of the investigator, preclude participation in the trial.
- 8. Subjects with lip tattoos, piercings, facial hair, or scars that would interfere with visualization of the lips and perioral area for the effectiveness assessments.
- 9. Subjects with abnormal lip function, with inability to effectively sip water through a straw.
- 10. Subjects with abnormal lip sensation with inability to feel a 0.4G monofilament or a cotton wisp at any site on the lip.
- 11. Subjects with moderate or severe abnormal lip asymmetry.

- 12. Subjects with any mass formation on the lip.
- 13. Subjects with dentures or any device covering all or part of the upper palate, and/or severe malocclusion or dentofacial or maxillofacial deformities as judged by the Treating Investigator. Subjects planning to undergo extensive dental procedures such as dental implants, multiple tooth extractions, or oral surgery should not participate. Minor dental procedures such as teeth cleaning and repair of caries are not exclusionary.

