- 10. If blanching of the tissues is observed during or directly after injection and becomes a concern, the area may be gently massaged. If blanching persists, contact the Medical Monitor.
- 11. The lips should be augmented to achieve the maximum desirable appearance for both the treating investigator and the subject. Subjects should be provided a small hand mirror to observe the results and further injections conducted until maximum benefit has been obtained. Care should be taken to ensure that the lips are symmetric from right to left and that the upper and lower lips have relative proportionality.
- 12. The perioral area should be corrected AFTER the upper and lower lips have been corrected. Some correction of perioral rhytids may occur with lip augmentation, thus it is best to address any remaining perioral correction needs after the lip injections have been completed.
- 13. If the treated area is swollen directly after the injection, an ice pack can be applied on the site for a short period if the investigator deems it appropriate. Ice should be used with caution if the area is still numb from anesthetic to avoid thermal injury.
- 14. Subjects should be encouraged to avoid a recumbent position for several hours after injections to reduce swelling. The use of ice, cold packs or other therapies to reduce swelling should only be performed at instruction of the investigator. The subject should be instructed to contact the site if substantial swelling occurs.

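### The 10-day post-injection limit on clotting-impairing agents in exclusion 6 is not carried into the on-study medication rules, and section 7.4.7.3 read literally allows those agents

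*Combined protocol and SAP*

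**What the plan says.** Exclusion 6 (section 7.3.2, repeated in the synopsis) concerns a subject's ability to withhold thrombolytics, platelet inhibitors, NSAIDs such as aspirin and ibuprofen, and other products that slow clotting, "within 10 days before AND after any injection session".

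Four later sections govern medication or behaviour after enrolment:

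- Section 7.4.7.1 opens with "Subjects should be given the following additional instructions" and gives two, on sun and cold exposure and on skin procedures.
- Section 7.4.7.2 opens with "Subjects will be advised to avoid the following for the duration of the study" and lists six items. One of them is "Other hyaluronic acid filler materials or collagen-based filler materials below the orbital rim".
- Section 7.4.7.3 sets the converse rule: "Permitted medications/treatments include any concomitant medication/treatment not listed below". It then lists five items.
- Section 7.4.3 (injection techniques, item 14) gives post-injection advice on posture and ice, beginning "Subjects should be encouraged to avoid a recumbent position for several hours after injections to reduce swelling".

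Section 7.4.7 covers recording. It says "All medications taken on a regular basis, including vitamins, aspirin, and acetaminophen, should be recorded", and the sentence goes on to place that recording before the device is used. It also requires any concomitant drug to relate to "documented medical history, prophylaxis, or an AE".

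**The concern.** An exclusion criterion is applied once, at the Visit 1 eligibility review. The pre-injection half of the window has passed by then and can be checked. The post-injection half is still to come, so it needs an on-study rule if it is to be followed uniformly at five sites. None of the on-study sections supplies one, and 7.4.7.3 goes further than silence because it permits whatever its list leaves out. A site that relies on that section could allow ibuprofen on Day 2 and believe it was following the protocol.

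What is at stake is subject safety and the cleanliness of the injection-site adverse event data. Safety of repeat injection is a study objective, and treatment-emergent adverse events are the safety endpoint. The device instructions in Appendices 2 and 3 already name bruising and bleeding as risks, and they note that patients who had thrombolytics, anticoagulants or platelet inhibitors in the 3 weeks before treatment have not been studied.

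**Working it through.** The plan gives no figure to reproduce. The check compares texts and day windows.

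**1. Where exclusion 6 agents appear after enrolment**

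| Section | Items | Naming an exclusion 6 agent as restricted |
|---|---|---|
| 7.4.7.1 Precautions | 2 | 0 |
| 7.4.7.2 Prohibited | 6 | 0 |
| 7.4.7.3 Exceptions to the permitted rule | 5 (all repeated from 7.4.7.2) | 0 |

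The distinct items number 2 + 6 = 8, and none restricts these agents. Item 14 of the injection techniques does not either. Aspirin after injection is mentioned in Appendix 1, but as emergency treatment for skin infarction, visual symptoms or stroke.

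**2. The two lists compared.** Section 7.4.7.2 has 6 bullets and 7.4.7.3 has 5, so 6 − 5 = 1 is missing: the hyaluronic acid and collagen filler bullet. Taken literally, 7.4.7.3 permits what the section before it prohibits.

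**3. Does the omission look deliberate?** The forward-looking parts of exclusions 14, 15, 16, 18 and 19 each have a matching bullet in 7.4.7.2, and the fillers in exclusion 17 have one too. Exclusion 6, which states a post-injection window outright, has none. The match is not complete elsewhere: planned dental work in exclusion 13 also lacks a bullet. The pattern therefore suggests an oversight without proving one.

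**4. Can existing contacts cover the window?** Treatment is on Day 1.

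- Post-injection window: Day 1 to Day 1 + 10 = Day 11.
- Day 3 call: 3 ± 2 = Days 1 to 5, inside the window.
- Day 14 call: 14 ± 2 = Days 12 to 16, the first contact after it closes.
- Diary: two weeks after treatment, to Day 1 + 14 = Day 15, so it spans the window.

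Both calls review concomitant medications and also confirm adherence to prohibited treatments (section 7.7.2). Together they can cover all of Days 1 to 11. At present the adherence question has no exclusion 6 entry to check against, while the medication review would still bring out the use.

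**5. Effect on results.** The Day 1 pain scores are taken immediately and 15 minutes after injection, so agents used in the days afterwards cannot alter them. For adverse events, the documents give neither a frequency of use nor an added risk, so no effect size can be calculated.

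**The case against.** The strongest reply is that exclusion 6 has no purpose unless withholding is expected. Its window is specific and emphasised, and a sensible investigator would let it prevail over a generic catch-all, just as the express filler ban in 7.4.7.2 should prevail over 7.4.7.3. Much of this stands. It lowers the practical risk, but the literal conflict remains.

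A reader might also infer several stronger points that the documents do not support:

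- **That section 7.4.7 endorses aspirin, or NSAIDs for lip pain.** The aspirin sentence is a baseline recording rule. The requirement that a drug relate to history, prophylaxis or an adverse event is a necessary condition and grants no permission.
- **That the calls would miss such use.** The same calls review concomitant medications.
- **That use would not be a protocol departure.** The protocol does not define a deviation, and section 7.3.3 leaves significant violations to the sponsor or medical monitor.
- **That subjects are never told to withhold.** The consent pages are not in our copy, nor are the contents of the diary card and the special-interest event letter. Instructions may be given there.

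**Conclusion.** The point holds as a low-severity inconsistency. The post-injection half of exclusion 6 is not carried into 7.4.7.1 or 7.4.7.2, and the catch-all in 7.4.7.3, read literally, permits the agents concerned. The dropped filler bullet is a drafting conflict in the same section, and its risk is limited to sites reading the rule differently.

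The consequence is small. Use would be recorded, the diary captures adverse events through the window, bruising and swelling are already listed as expected events (section 7.9.3.1), and safety is summarised descriptively (section 8.1). It would go too far to conclude that the safety comparison is biased, because nothing in the documents shows how often these agents would be used, what risk they would add, or whether use would differ between arms.

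The conclusion assumes that the protocol text is what sites work from. If subject-facing material already instructs withholding, the practical gap is smaller still, although the wording of 7.4.7.3 would continue to contradict it.

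**What to change.** 1. Add a bullet to 7.4.7.2 prohibiting the exclusion 6 agents through 10 days after injection, except for emergency or medically necessary treatment, including the aspirin in Appendix 1. The bullet needs its own window because the section's lead-in applies to the whole study. Check it at the existing Day 3 and Day 14 calls.
2. Replace the list in 7.4.7.3 with a statement that any concomitant medication or treatment not prohibited in 7.4.7.2 is permitted. One list then governs, and the filler conflict disappears.

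The cost is a protocol amendment, which needs sponsor and IRB approval before implementation (sections 9.2 and 10.5). No study procedure is added. Subjects would have no NSAIDs for lip pain for 10 days, which exclusion 6 already implies. Acetaminophen is not named in exclusion 6 and stays available.

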### 7.4.8 Assessment of Compliance

Administration of the study device by the investigator is documented on the CRF.

### 7.5 Study Schedule

The visit-by-visit schedule of study activities is provided in Section 2. The timing of each visit is relative to Day 1, which is defined as the day the subject is treated in PRO 2019-02.

All visits should be performed within the windows specified on the schedule of study activities. Every attempt should be made to have each subject attend each visit as scheduled. If a subject is unable to attend a visit within the specified window the visit should be scheduled as closely as possible to the applicable window.

### 7.6 Study Procedures

The schedule of study activities summarizes the study procedures to be performed at each visit. Individual study procedures are described below.

All clinical assessments (LFGS, POL, iGAI, lip function, lip sensation, lip texture, lip firmness, lip symmetry, and lip movement/function evaluations) must be conducted by qualified investigators listed on Form FDA 1572 who have been delegated these tasks by the principal investigator (PI). The PI may delegate this task only to physicians, physician assistants, or nurse practitioners who have documented training for this protocol and past experience conducting the assessment.

To minimize variability of evaluations, the same investigator/sub-investigator should perform these assessments for any given subject and anticipate evaluating the subject at each visit, to the extent possible.

## 7.6.1 Study Roles

Each site will designate at least one Treating Investigator who is either a board certified dermatologist or board certified plastic surgeon and at least one blinded Evaluating Investigator. In addition, one or more members of the study site staff may be designated as unblinded for the purposes of assisting in the management of study device use. Any study staff designated as unblinded should have no direct contact with subjects and may not perform any subject evaluations, assessments or measurements (including vital signs, questionnaires, etc.). Designation of unblinded study staff will be recorded in the Delegation of Authorities Log form.

The Treating Investigator will be responsible for conducting the injections, ensuring that the correct randomized study device and topical product is administered in accordance with the protocol and other study instructions. Any AEs brought to the attention of the Treating Investigator will be forwarded to the blinded Evaluating Investigator for final adjudication and documentation.

The blinded Evaluating Investigator will be responsible for assigning grades for the various parameters (LFGS, POL, iGAI, lip function, lip sensation etc.). The blinded Evaluating Investigator will be responsible for recording AEs and determining their severity and relationship to the study device or the injection procedure.

## 7.6.2 Written Informed Consent

The study personnel will review the ICF for this study with each subject and give the subject an opportunity to have all questions answered before proceeding with any study procedures. A copy of the signed ICF will be given to every subject and the original will be maintained with the subject's records. The study personnel will review the letter regarding AESI dated 04JUN19, have the subject sign the letter. A copy of the signed letter will be given to every subject and the original will be maintained with the subject's records.

## 7.6.3 Significant Medical History/Demographic Information

Medical history and demographic information will be updated if/as needed at Visit 1/Day 1 to record any changes since Visit 1 in Protocol PRO 2018-02.

### 7.6.4 Vital Signs

Vital signs will be recorded. Vital signs will include sitting blood pressure, temperature, heart rate, and respiratory rate.

#### 7.6.5 Vision Evaluations

Subjects will be assessed with Snellen visual acuity, confrontational visual fields, and ocular motility by a trained evaluator. These assessments will be performed at Visit 1/Day 1 prior to treatment and repeated 30 minutes following treatment and at Visit 2/Month 1. Normal and abnormal findings are summarized in Appendix 5.

## 7.6.5.1 Snellen Visual Acuity

Site staff trained on conducting visual acuity will hold the provided Snellen chart 6 feet from the subject. The subject will be instructed to wear any usual corrective eyewear and cover one eye with the provided occlude. The subject will read each line until no longer capable. The best readable line will be recorded for each eye.

Normal finding: The same Snellen Visual Acuity results as the Snellen Visual Acuity results recorded pre-treatment at Visit 1/baseline in PRO 2018-02.

Abnormal finding: Any change from the Snellen Visual Acuity results recorded pre-treatment at Visit 1/Baseline in PRO 2018-02 will be considered abnormal.

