#### 7.9.3 Definitions of Terms

#### 7.9.3.1 Adverse Event

An AE is defined as any untoward medical occurrence associated with the use of a drug/device in humans, whether or not considered drug/device-related (21 Code of Federal Regulations [CFR] 312.32 (a) and 803). An AE can therefore be any unfavorable and unintended sign (including an abnormal laboratory finding, for example), symptom, or disease temporally associated with the use of a drug/device, without any judgment about causality.

Expected adverse events are defined as the events that appeared at injection site subsequent to the first injection. Expected adverse events may include but are not limited to bruising, swelling, erythema, edema, and inflammation at injection site.

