#### 7.9.3.4 Adverse Events of Special Interest

Certain events will require more detailed and timely reporting. These include:

- any significant changes in vision. A one-line change in the Snellen chart is considered significant and requires reporting as an AESI.
- any events attributable to an embolic or ischemic cause (e.g., skin infarction)
- Any incidence of an event due to an embolic or ischemic cause or visual disturbances (including, but not limited to, any loss of vision, blurry vision, double vision, pain in or around eye, blind spot or shadow in the visual field, trouble moving eyes, etc.) MUST be immediately reported to the Medical Monitor by phone, email or fax. The investigator/coordinator must complete the AE source/CRF page and email or fax it to the Medical monitor as soon as possible after the investigator or coordinator has become aware of its occurrence. These reports will include the depth of injection, the injection volume, the symptoms that were observed, the time to onset, time to resolution, and any

interventions that were implemented. The Sponsor will notify the FDA within 10 working days regardless of relation to investigational device.

In the event of blindness or any ophthalmic signs or symptoms, subjects will undergo immediate evaluation by a retina specialist.

Refer to Appendix 1: Filler First Aid Protocol.

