#### 18 APPENDIX 5: VISION EVALUATION RESULTS

## **Snellen Visual Acuity**

Normal findings: The same Snellen Visual Acuity results as the Snellen Visual Acuity results recorded pre-treatment at Visit 1/baseline in PRO 2018-02.

Abnormal findings: Any change from the Snellen Visual Acuity results recorded pre-treatment at Visit 1/baseline in PRO 2018-02 will be considered abnormal.

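### The Snellen rule gives no direction, so a one-line gain is literally an exclusion at Visit 1 and an AESI after treatment, which does not fit the protocol's own definition of an adverse event

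*Combined protocol and SAP*

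**What the plan says.** - Section 7.6.5.1 defines a normal Snellen result as one identical to the pre-treatment reading at Visit 1 of PRO 2018-02. Everything else is abnormal: "Any change from the Snellen Visual Acuity results recorded pre-treatment at Visit 1/Baseline in PRO 2018-02 will be considered abnormal". Appendix 5 says the same: "Any change from the Snellen Visual Acuity results recorded pre-treatment at Visit 1/baseline in PRO 2018-02 will be considered abnormal". Neither gives a direction or a tolerance.
- The unit of measurement is the line, for each eye separately: "The best readable line will be recorded for each eye".
- Section 7.9.3.4 lists significant changes in vision as AESIs and adds: "A one-line change in the Snellen chart is considered significant and requires reporting as an AESI". It gives no direction and no visit from which the change is counted.
- Exclusion 5 (section 7.3.2 and synopsis) applies the same definition before treatment, barring subjects with "abnormal Snellen Visual Acuity at Visit 1 pre-treatment as defined in section 7.6.5 and Appendix 5".
- Section 7.6.5 schedules the vision tests before treatment, and then "repeated 30 minutes following treatment and at Visit 2/Month 1".
- Section 7.9.3.1 opens its definition with "An AE is defined as any untoward medical occurrence associated with the use of a drug/device in humans" and continues: "An AE can therefore be any unfavorable and unintended sign".
- Section 8.3 plans a separate summary of visual TEAEs by preferred term.

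**The concern.** An AESI is by name a kind of adverse event, and the protocol's adverse event has to be untoward or unfavorable. Reading one line better is neither, yet the Snellen and AESI wording covers it. A site cannot follow all these sections literally.

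Two things are at stake. First, the vision-safety summary could mix improvements with deteriorations, because nothing in section 8.3 separates them. A reader of the AESI count or the visual TEAE table could not tell how many entries describe a loss of acuity. Second, a subject who reads one line better at Visit 1 than in PRO 2018-02 is excluded on the literal text, from a pool that the synopsis already expects to be below 158.

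**Working it through.** The plan states no retest rate or expected number of vision flags, so there is no figure of its own to reproduce. The check has a textual part and an illustration.

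**Text**

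1. Only the best readable line is recorded, so the smallest recordable change is one line.
2. Every post-treatment result that is abnormal under section 7.6.5.1 is therefore at least a one-line change. It meets the section 7.9.3.4 wording if that section uses the same reference reading.
3. A one-line gain satisfies both rules, and at Visit 1 it satisfies exclusion 5. It does not satisfy section 7.9.3.1.
4. No section limits the Snellen rule to worsening.

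**Illustration**

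Inputs:
- two eyes (section 7.6.5.1) and two post-treatment tests (section 7.6.5), giving four comparisons per subject
- N = 158 as an upper bound, since the synopsis expects fewer
- *q*, the chance that one eye at one test differs by a line with no true change. This is **an assumption**, taken from 1% to 20% and split equally between better and worse.

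Formulas for the chance that a subject has at least one post-treatment flag:
- eyes independent: 1 − (1 − q)^4
- eyes fully correlated (both change together, so two comparisons): 1 − (1 − q)^2
- losses only: replace q by q/2

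| q | Any direction, independent | Any direction, correlated | Losses only, independent | Losses only, correlated | Expected flagged of 158, any direction (correlated to independent) |
|---|---|---|---|---|---|
| 1% | 3.9% | 2.0% | 2.0% | 1.0% | 3.1 to 6.2 |
| 5% | 18.5% | 9.8% | 9.6% | 4.9% | 15.4 to 29.3 |
| 10% | 34.4% | 19.0% | 18.5% | 9.8% | 30.0 to 54.3 |
| 20% | 59.0% | 36.0% | 34.4% | 19.0% | 56.9 to 93.3 |

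Example at q = 20%, independent eyes: 1 − 0.8^4 = 1 − 0.4096 = 59.0%; losses only, 1 − 0.9^4 = 1 − 0.6561 = 34.4%.

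Half of the flagged readings are gains by assumption. The share of flagged subjects who have gains only is (any − losses)/any. With independent eyes this is about 50% at q = 1% and (59.0 − 34.4)/59.0 = 42% at q = 20%.

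Exclusion 5, with one test and two independent eyes: 1 − (1 − q)^2 = 2.0% at q = 1% and 36.0% at q = 20%. Losses only: 1.0% and 19.0%.

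**Sensitivity to screening**

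The formulas ignore that exclusion 5 has already removed subjects whose reading moved. A simulation allowed for this. It used two independent eyes, true acuity spread evenly between two lines, normal reading error rounded to the nearest line, and kept only subjects whose Visit 1 reading matched in both eyes.

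| Per-eye disagreement | Flagged after treatment | Flagged for gains only | 1 − (1 − q)^4 at the same rate |
|---|---|---|---|
| 5.6% | 9.5% | 4.7% | 20.6% |
| 17.0% | 30.6% | 14.6% | 52.5% |

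Screening lowers the number of flags, but about half of the flagged subjects still have gains only.

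**The case against.** **The protocol surely means worsening.** The further examples in section 7.9.3.4 are all adverse, the visual-field and motility tests define abnormal as a deficit, and the suspension rule in section 7.9.9 speaks of vision loss. Read together with section 7.9.3.1, gains would drop out. This is a fair account of likely intent, and a reader should not infer that the sponsor set out to count gains as harm. But the intent is nowhere written, and sites work from the text.

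**An abnormal finding is not automatically a TEAE.** The blinded Evaluating Investigator decides what is recorded as an AE (section 7.6.1). This stands in part: gains could enter the visual TEAE table, but it is not shown that they would. The AESI sentence, however, requires reporting and leaves no such discretion.

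**The numbers are assumed.** This stands. A reader might infer that test variation would dominate the vision results and hide a true event. The documents do not support that. The retest rate is unknown, independence of eyes and tests is assumed, and screening removes unstable readers. A true event would also have other routes to notice: visual fields, motility, vision questions at every telephone contact, and the clinical detail required in AESI reports. With 1:1:1 randomization the noise should be similar across arms, so it dilutes the counts rather than biasing the comparison.

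**The old reference reading.** A reader might infer that measuring from PRO 2018-02 instead of this study's Visit 1 distorts the post-treatment results. While exclusion 5 stands it does not, because a correctly enrolled subject's Visit 1 reading equals the PRO 2018-02 reading. The age of the reference matters for eligibility. Section 7.9.3.4 still names no reference visit.

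**Fixing direction does not remove the noise.** Correct: chance losses would remain flagged, as the losses-only columns show.

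**Conclusion.** The contradiction stands on the text alone and needs no assumption. Sections 7.6.5.1 and 7.9.3.4, Appendix 5 and exclusion 5 cover a one-line gain, and section 7.9.3.1 does not allow it to be an adverse event.

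Its numerical size is illustrative. For an assumed 1–20% chance change per eye per test, about 4–59% of subjects would carry at least one post-treatment flag with independent eyes and about 2–36% with fully correlated eyes. Allowing for screening would lower these figures. Roughly half would be gains if the noise is symmetric. The consequence is a vision-safety summary that pools improvements with losses to a similar degree in every arm. Neither a biased comparison nor a masked safety signal is shown.

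**What to change.** 1. Reconcile sections 7.6.5.1 and 7.9.3.4, Appendix 5 and exclusion 5 (synopsis and section 7.3.2) with section 7.9.3.1 on the direction of change.
2. State in section 7.9.3.4 the visit from which the one-line change is measured.
3. Leave to the sponsor and medical monitor which findings exclude a subject and which are reported as AESIs. This review does not propose that rule.
4. Whatever rule is chosen, record the direction of each Snellen change on the CRF and specify in the SAP that losses and gains are tabulated separately by arm, so that gains are not pooled with losses in the vision-safety summary.

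Cost: small wording and CRF changes and one extra table split. Chance losses will still be flagged, so the loss table should be read with that in mind.
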